NCT 02749045

Date: 5/2016

Title: The Simultaneous Assessment of Invasive Fractional Flow Reserve and SPECT Myocardial Ischemia Using Regadenoson in the Catheterization Laboratory.

[name] [name]; [name] (Nuclear Cardiology)
[name]; [name] (Intervention Cardiology)

Background: Coronary revascularization guided by either invasive Fractional Flow Reserve (FFR) measurement or the presence and extent of myocardial ischemia on stress testing is associated with better outcome compared to coronary anatomy-based revascularization(1). The appropriate use criteria (AUC) increasingly emphasize the importance of establishing the functional significance of coronary lesions prior to percutaneous coronary interventions (PCI)(2). Myocardial ischemia is most often assessed by myocardial perfusion stress- single-photon emission computed tomography (MPS). However, FFR and MPS-derived ischemia measures do not always correlate, and disparities are known to exist in as many as 40% of cases (3). While the complex interplay between focal epicardial disease, diffuse epicardial disease and microvascular disease is the physiological basis for these disparities, technical factors including temporal and protocol differences between FFR estimation and ischemia estimation may also play a role. Initial validation studies found high correlation between stenosis with FFR <0.65 and myocardial ischemia in single vessel disease, while the contemporary practice is to attribute hemodynamic significance to FFR <0.80 (4,5). Furthermore these original studies were performed using dipyridamole or adenosine stress, which have different hyperemic flow profiles compared to regadenoson (6). This study aims to determine the correlation between simultaneous FFR and MPS obtained using regadenoson in the catheterization laboratory. The protocol is designed to eliminate temporal and stress protocol differences between FFR and MPS. Our group has previously validated the use of regadenoson for FFR estimation (7).

Aims:

1. To determine the correlation between FFR and ischemia (presence and extent) assessed simultaneously in the catheterization laboratory using regadenoson.
2. To determine the optimal cut off of FFR with regadenoson stress that predicts the presence of myocardial ischemia on MPS

Methodology:

Study Population:

Inclusion criteria:

Fifty patients aged ≥ 18 years, undergoing clinically-indicated FFR measurement (to determine the hemodynamic significance of intermediate degrees of stenosis) for single or two –vessel epicardial coronary disease during diagnostic coronary angiography for suspected coronary artery disease will be recruited. Patients with prior coronary stents will be included if they fulfill criteria. Patients with prior SPECT will be included if they provide informed consent to undergo another SPECT study as described in the protocol.

Exclusion criteria:

1. Patients with 3-vessel disease
2. Prior CABG
3. Patients with second or third- degree AV block, or sinus node dysfunction without a functioning pacemaker
4. Patients who have ingested caffeine-containing products within the past 12 hours.

Study Design:

Informed consent will be obtained prior to diagnostic coronary angiography. Based on current coronary angiography and FFR volumes and a conservative estimate, it is anticipated that we will need to screen (with consent) 500 patients in order to recruit 50 who will have FFR assessment.

Standard procedure will be followed for FFR testing using regadenoson. Regadenoson will be injected as a 10-15 sec bolus followed by a saline flush. Patients will have an injection of Tc-99m sestamibi 10-20 seconds after the saline flush (to mirror the standard stress testing protocol). A weight-based dosing scheme for Tc-99m will be used (30mCi for patients weighing up to 200 lbs; additional 5 mCi for every 50 lbs over 200 lbs). Standard protocol for regadenoson-stress MPS will be performed. A minimum of 2 mins will be allowed to elapse between radiotracer administration and percutaneous coronary intervention (PCI), if indicated, to allow complete extraction of the radiotracer, and an accurate assessment of perfusion defect size. In patients with 2-vessel disease, who require FFR testing in both vessels, radiotracer injection will be performed during FFR testing of the more severe stenosis, as assessed by visual inspection of the coronary angiogram.

Patients will be brought to the nuclear cardiology laboratory 1-3 hours following the coronary angiogram (\pm coronary intervention) for a standard SPECT acquisition. Since the perfusion data will pertain to the time of tracer injection, patients could be vascularized as clinically indicated prior to the SPECT acquisition.

Patients will be monitored for 2-6 hours, or overnight, as clinically indicated following diagnostic coronary angiography and PCI, respectively.

A low dose resting MPS will be performed the next day, if the stress MPS is abnormal.

SPECT Analysis:

Perfusion image analysis will be performed using a standard 17 segment model and polar plots. Quantitative perfusion defect analysis using the QGS (Cedars-Sinai Medical Center, CA) will be used to determine the Total Perfusion Defect size, which will be the parameter used for analysis. Image interpretation will be performed by physicians blinded to the results of FFR testing.

Statistical Analysis:

Standard statistical tests to correlate FFR with the presence and extent of MPS will be applied to patients groups with concordant and discordant FFR/SPECT studies. The percentage of patients with concordant FFR and SPECT results will be determined. The characteristics of patients with discordant FFR and SPECT results will be described (mean FFR and range of FFRs, single vs. two- vessel disease, lesion characteristics such as diffuse vs. discrete disease). An ROC curve analysis will be performed to define the cut-off of FFR that optimally predicts SPECT ischemia.

Adverse event monitoring:

All study procedures are clinically indicated except the Tc-99m injection and SPECT acquisition, which are clinically approved procedures. Any adverse events will be reported.

References

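### Infarction in the territory of the FFR vessel is neither excluded nor recorded, and the SPECT measure as written would count fixed scar as ischemia

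*Combined protocol and SAP*

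**What the plan says.** **Eligibility (Methodology, Study Population).** The plan enrols "Fifty patients aged ≥ 18 years, undergoing clinically-indicated FFR measurement" for intermediate stenosis in one or two vessels, "during diagnostic coronary angiography for suspected coronary artery disease will be recruited". On earlier stenting it says: "Patients with prior coronary stents will be included if they fulfill criteria". The exclusions are:

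- "Patients with 3-vessel disease";
- earlier bypass surgery;
- "Patients with second or third- degree AV block, or sinus node dysfunction without a functioning pacemaker";
- "Patients who have ingested caffeine-containing products within the past 12 hours".

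No criterion mentions infarction, known scar, or why and where a stent was placed.

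**SPECT measure (Study Design and SPECT Analysis).** Total perfusion defect size is named as the analysis parameter. On rest imaging the plan says: "A low dose resting MPS will be performed the next day, if the stress MPS is abnormal". It does not say how the rest scan enters the analysis.

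**Analysis (Aims and Statistical Analysis).** Aim 1 correlates FFR with the presence and extent of ischemia. Aim 2 is "To determine the optimal cut off of FFR with regadenoson stress that predicts the presence of myocardial ischemia on MPS". The plan also reports the percentage of concordant patients and describes the discordant ones by FFR values, number of diseased vessels and lesion characteristics. Infarct history is not among the items named.

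**The concern.** A patient stented for an earlier infarct who now has an intermediate stenosis in the same artery meets every criterion. The scar can appear as a perfusion defect on the stress scan whatever the present stenosis does to flow. If total defect size is the outcome, that patient is SPECT-abnormal for a reason other than stress-induced ischemia, so the reference standard for both aims is misclassified.

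This matters more here than in a general accuracy study. The Background says the protocol is built to remove timing and stress-protocol differences between the two tests. It attributes the remaining disagreement to focal, diffuse and microvascular disease. Scar is a further cause that it does not name. The error runs in one direction, so a larger sample would not remove it. Without infarct history by territory, discordance caused by scar may not be recognised when the discordant patients are described.

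**Working it through.** The sample size of 50 comes with no power or precision target, so there is no figure of the plan's own to reproduce. The documents give neither an infarct share nor a threshold for a positive SPECT. Everything below except n = 50 is assumed and serves only to show scale.

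**Step 1. Scar patients placed at random with respect to FFR.** Assume a bivariate normal latent correlation of 0.65, with both tests called positive beyond 0.4 SD. The probabilities are then:

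- SPECT positive: π = 0.345;
- both tests positive: 0.218;
- both tests negative: 0.529;
- each kind of discordance: 0.126.

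Concordance is 0.218 + 0.529, about 0.748 before rounding, and the AUC is 0.808. Let a fraction q of patients be SPECT-positive because of scar, whatever their FFR.

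- Discrimination shrinks by k = π / [π + q(1 − π)], so AUC′ = 0.5 + k(AUC − 0.5).
- Concordance′ = 0.748 − q(0.529 − 0.126).

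| Scar patients | q | k | AUC | Concordance |
|---|---|---|---|---|
| 0 of 50 | 0 | 1 | 0.808 | 74.8% |
| 2 of 50 | 0.04 | 0.345/0.371 = 0.929 | 0.5 + 0.929 × 0.308 = 0.786 | 74.8 − 1.6 = 73.2% |
| 5 of 50 | 0.10 | 0.345/0.4105 = 0.840 | 0.5 + 0.840 × 0.308 = 0.759 | 74.8 − 4.0 = 70.8% |

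Simulation at n = 50 (4,000 replicates) agrees: AUC 0.786 with 2 scar patients and 0.756 to 0.759 with 5; concordance 73.2% and 70.7 to 71.0%.

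**Step 2. Does the cut-off move?** The false-positive rate is unchanged. Sensitivity becomes a weighted mean of the old sensitivity and the false-positive rate. Hence Youden J′ = k × J at every cut-off. Multiplying the curve by a constant leaves its maximum in the same place.

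**Step 3. A second model that lets scar raise FFR.** Assumptions (400,000 patients per scenario):

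- FFR ~ N(0.82, 0.08);
- ischemic defect = 60(0.80 − FFR) + 5, noise SD 4, floored at 0;
- SPECT positive at 5% or more, FFR positive at 0.80 or less;
- mean scar 6, 10 or 15% of myocardium (SD 4);
- FFR raised by 0, 0.03 or 0.05 in infarct patients, with their ischemic defect cut by 30% when the rise is above 0.

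| Outcome analysed | Infarct share | r | Concordance | Youden cut-off |
|---|---|---|---|---|
| Total defect | 0% | −0.73 | 78% | 0.815 |
| Total defect | 10% | −0.66 to −0.41 | 73 to 76% | 0.81 to 0.815 |
| Total defect | 20% | −0.62 to −0.26 | 67 to 74% | 0.805 to 0.815 |
| Total defect | 30% | −0.59 to −0.18 | 61 to 71% | 0.805 to 0.815 |
| Scar subtracted (mean scar 10%) | 10 to 30% | −0.73 | 78 to 79% | 0.81 to 0.825 |

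A further run with scar subtracted (10 to 20% infarcts, FFR raised by 0.03 to 0.05) gave r between −0.70 and −0.72 and a cut-off higher by at most about 0.01. Total defect size therefore carries the damage, and subtracting scar removes nearly all of it.

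**Step 4. Precision at n = 50.** The 95% interval for 70% concordance (Wilson) is 56 to 81%. For |r| = 0.5 (Fisher z) it is 0.26 to 0.68.

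**The case against.** The best defence is that the plan already has the remedy to hand. A rest scan is made whenever the stress scan is abnormal, and both the aims and the ROC analysis speak of ischemia. A sensible analyst might therefore separate fixed from reversible defects. Step 3 supports this: with scar subtracted, the results match those of an infarct-free cohort. It stands as an account of what would cure the problem. It does not show that the plan does so, because the named parameter is total defect size and no subtraction is stated.

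Second, the effect may be small. With 2 scar patients the loss is about 0.02 in AUC and 1.6 points of concordance. Even the loss with 5 is below the sampling SD at n = 50 (about 0.066 and 6 points). That limits the weight of the point, although a one-directional bias is different in kind from sampling error.

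Third, keeping such patients is defensible. The study describes patients sent for clinically indicated FFR, and an exclusion would narrow applicability and cost recruits. This stands.

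A reader might infer four stronger things, none of which the documents support:

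- **Scar pulls the optimal FFR cut-off upward.** Step 2 shows no movement. For total defect, Step 3 shows it flat or slightly lower.
- **Using the rest scan would not help because FFR itself is shifted in an infarct territory.** The documents give no size for such a shift, and its modelled effect is small once scar is subtracted.
- **Patients with acute infarction will be enrolled.** No criterion bars them, but recruitment at diagnostic angiography for suspected disease makes this the weakest part.
- **Admitting stents means admitting many infarcts.** The quoted sentence concerns stents only, and no infarct share is given.

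**Conclusion.** The point holds in a limited form. Eligibility leaves infarction in the study-vessel territory open, and the analysis text does not remove fixed defects. Followed as written, scar is counted as ischemia, and correlation, concordance and ROC discrimination are weakened. With 2 to 5 such patients among 50, the AUC falls by about 0.02 to 0.05 and concordance by about 2 to 4 points. This rests on an assumed latent correlation of 0.65, about 34% of patients truly SPECT-positive, and scar unrelated to FFR. The true infarct share is unknown, and larger shares or larger scars would do more harm. No shift in the cut-off is shown; the most that can be said is that the cut-off rests on weaker discrimination. This is a worthwhile, inexpensive improvement and not a flaw that invalidates the design.

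**What to change.** 1. At enrolment, record infarct history by coronary territory (clinical history, Q waves, known scar on imaging).
2. Prespecify that the Aim 1 correlation, the concordance percentage and the Aim 2 ROC are reported for patients without infarction in the territory of the studied vessel, with the full-cohort result alongside.
3. State that where a rest scan exists, SPECT ischemia is the stress-minus-rest defect.
4. Add infarct history to the characteristics described in discordant patients.

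The cost is one baseline field, a few sentences of analysis text, and an infarct-free analysis set slightly below 50. No recruits are lost. Excluding infarction in the study territory is an option if the investigators prefer a cleaner cohort, at the price of some recruits and of results that no longer cover infarct vessels. It is not needed to resolve the point.

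### Total Perfusion Defect size is not tied to the territory of the vessel whose FFR is measured at tracer injection, so some two-vessel patients can be mislabelled

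*Combined protocol and SAP*

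**What the plan says.** All references are to the combined protocol and SAP.

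- **Inclusion criteria:** patients have clinically indicated FFR "for single or two –vessel epicardial coronary disease during diagnostic coronary angiography". Three-vessel disease and prior CABG are excluded. The expected share of two-vessel patients is not given.
- **Study Design:** if both vessels need FFR, "radiotracer injection will be performed during FFR testing of the more severe stenosis, as assessed by visual inspection of the coronary angiogram". The same section relies on timing: "Since the perfusion data will pertain to the time of tracer injection".
- **SPECT Analysis:** "Perfusion image analysis will be performed using a standard 17 segment model and polar plots". Quantitative software is then used to "determine the Total Perfusion Defect size, which will be the parameter used for analysis".
- **Statistical Analysis:** "The percentage of patients with concordant FFR and SPECT results will be determined", and "An ROC curve analysis will be performed to define the cut-off of FFR that optimally predicts SPECT ischemia". Vessel count appears only as one descriptor of discordant patients.
- **Background:** "The protocol is designed to eliminate temporal and stress protocol differences between FFR and MPS". Nothing is said there about location.

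No section assigns segments to coronary vessels, limits the defect to one vessel's territory, or states which FFR value enters the analysis when two are measured.

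**The concern.** FFR describes one stenosis. An unqualified total defect covers the myocardium supplied by every vessel. Call the vessel being tested when tracer is given the index vessel. In a two-vessel patient, a defect caused by the other vessel is then scored against the index FFR. The same gap applies if only one of two diseased vessels has FFR.

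Two errors can follow when the index territory is normal and the defect lies elsewhere:

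- **False discordance:** the index FFR is negative. This weakens the correlation and the AUC.
- **False concordance:** the index FFR is positive. The patient wrongly counts as agreement, which raises the AUC and partly offsets the loss.

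The correlation, the concordance percentage and the ROC analysis all use this pairing. The description of discordant patients by vessel count would also partly reflect the pairing rule rather than physiology. That matters because the study aims to strip out technical reasons for FFR and SPECT to disagree. The benchmark correlation cited in the Background came from single-vessel disease, where a second diseased vessel cannot produce this error.

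**Working it through.** **What can be reproduced.** The documents give no expected correlation, AUC, concordance or power. The 50 of 500 is a screening yield (10%). There is no plan figure to reproduce, so what follows is illustration on assumed inputs.

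**Step 1: a 2x2 check by hand.** Assume 40% of patients have index-territory ischemia, and FFR has 80% sensitivity and 80% specificity against it. Let f be the two-vessel share and q the probability of an independent defect in the other territory. Take f = 40% and q = 20%.

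- FFR negative, index territory normal: 0.60 × 0.80 = 0.48. FFR positive, index territory normal: 0.60 × 0.20 = 0.12.
- Fraction of these relabelled: f × q = 0.08.
- Falsely discordant: 0.48 × 0.08 = 0.0384, or 1.9 of 50. Falsely concordant: 0.12 × 0.08 = 0.0096, or 0.5 of 50.
- Concordance: 0.80 − 0.0384 + 0.0096 = 0.771.

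The mildest case (f = 20%, q = 10%) gives 79.3%. The strongest (f = 60%, q = 30%) gives 73.5%.

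**Step 2: how many SPECT labels change.** Now treat FFR severity and territory defect as standard normal, with latent correlation −0.6 between FFR and defect in each vessel. A cut-off of 0.5 SD makes 31% positive on each test. A whole-heart label is positive if either territory is. With independent vessels, the share changing label is f × (1 − p1) × p2. Here p1 = 0.309, and p2 is the upper normal tail beyond 0.5 + 0.6 × (SD by which the second vessel is milder).

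| Two-vessel share | Second vessel | p2 | Share changing label | Of 50 |
|---|---|---|---|---|
| 20% | 1 SD milder | 0.136 | 0.20 × 0.691 × 0.136 = 0.019 | 0.9 |
| 50% | 0.5 SD milder | 0.212 | 0.50 × 0.691 × 0.212 = 0.073 | 3.7 |
| 50% | equal | 0.309 | 0.50 × 0.691 × 0.309 = 0.107 | 5.3 |

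**Step 3: effect on AUC and discordance.** These results come from simulation with 400,000 patients per scenario, a 30-50% two-vessel share and between-vessel correlation of 0 or 0.3.

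| Scenario | Labels changed, of 50 | AUC, index territory | AUC, whole heart | Net rise in discordance |
|---|---|---|---|---|
| Second vessel 0.5-1 SD milder | 1.3-3.7 | 0.79 | 0.73-0.77 | 1.2-4.6 points |
| Second vessel equal | 3.0-5.3 | 0.79 | 0.71-0.75 | 3.1-6.6 points |
| Index vessel picked by visual grade; grade correlates 0.5-0.7 with FFR severity | see below | 0.78-0.79 | 0.75-0.78 | 1.0-3.4 points |
| As above, correlation 0.9 | 1.5-2.8 | change −0.001 to +0.002 | (near identical) | 0.2-0.4 points |

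Across visual-grade correlations of 0.3 to 0.9, 1.5-4.5 of 50 change label. At 0.9, false discordance (1.7-3.0% of patients) and false concordance (1.4-2.6%) nearly cancel. With only 20% two-vessel, AUC goes from 0.783-0.784 to 0.777-0.780 at a correlation of 0.7, with no loss at 0.9.

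**Step 4: discordance within two-vessel patients.** Ignoring how the index vessel is chosen, it is 26% against own territory and 30-35% against the whole heart when the second vessel is milder. With the injection rule modelled (visual-grade correlation 0.5-0.9), it is already 28-32% against own territory. The whole-heart measure then adds about 1 to 7 points, and only about 1 at correlation 0.9.

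**Step 5: sampling error.** Hanley-McNeil, A = 0.79, with 15.5 positive and 34.5 negative patients (31% of 50).

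- Q₁ = A/(2 − A) = 0.653; Q₂ = 2A²/(1 + A) = 0.697; A² = 0.624.
- Variance = [0.166 + 14.5 × 0.0288 + 33.5 × 0.0732] / (15.5 × 34.5) = 3.036/534.75 = 0.00568.
- Standard error = 0.075.

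Every AUC change above is no larger than this.

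**The case against.** **The mismatch rests on inference.** The documents do not define the total defect as whole-heart, and do not say which FFR is paired with it. If the lowest FFR, or any positive FFR, were used, the errors would differ. This stands. What is certain is that the pairing rule is missing; that a remote defect will be charged to the index FFR follows only from the natural reading.

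**A patient-level analysis fits the aims.** Aim 2 concerns ischemia on SPECT generally, and concordance is counted in patients. The documents do not contradict themselves, which is also fair. But FFR remains lesion-specific, so the patient-level pairing is the weaker choice.

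**The design already limits the problem.** Three-vessel disease and prior CABG are excluded, tracer goes with the visually worse stenosis, and vessel count is described among discordant patients. These reduce the problem without removing it.

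**Territory assignment brings its own error.** Assume 10% of index-territory positives are lost and 10% of other-territory positives are wrongly captured, in all 50 patients, with 30% two-vessel. At a visual-grade correlation of 0.9, whole-heart AUC is 0.781-0.784 against 0.767-0.769 for territory. At 0.7 it is 0.772-0.776 against 0.768-0.769. With 50% two-vessel and a second vessel 0.5 SD milder, territory does better (0.768 against 0.732-0.751). This stands in part: the 10% is assumed, and about half or more of the loss disappears if restriction is applied only to two-vessel patients.

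**Stronger readings to avoid.** A reader might infer that the optimal FFR cut-off will be biased; no shift of consequence is shown. A reader might infer that AUC must fall; when the injection rule is modelled it falls in 41 of 48 scenarios, and it is essentially unchanged when visual grading is accurate. A reader might take the 26% against 30-35% contrast to mean that the vessel-count description is invalid; Step 4 shows that this overstates the effect, and the description is not a planned causal comparison.

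**Conclusion.** The point holds as a cheap improvement. The plan names a parameter that, read naturally, pairs a lesion-specific FFR with a whole-heart defect, and it leaves the choice of FFR unstated when two are measured. Some two-vessel patients would be mislabelled in either direction, and the vessel-count description of discordant patients would partly reflect the pairing rule.

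Confidence is high that the rule is missing and low on size. About 1 to 5 of 50 patients change SPECT label, and AUC changes by between about 0 and −0.07. This rests on 20-50% two-vessel, latent correlation −0.6, 31% positive, and a second vessel equal or milder or an index vessel chosen by visual grade. None of these inputs is in the documents. Larger effects would need a second vessel more severe than the index vessel. The documents do not support a claim that the study's main results would be materially wrong.

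**What to change.** Add to Statistical Analysis that the primary correlation, concordance and ROC analyses use one pair per patient:

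- the FFR measured at tracer injection; and
- in two-vessel patients, the defect size in that vessel's territory, taken from the planned 17-segment and polar-map data. Single-vessel patients may keep total defect size.

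State that segments are assigned to the vessel from the angiogram without sight of the perfusion result. Report two sensitivity analyses: whole-heart defect size in all patients, and single-vessel patients only.

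The cost is analysis wording and modest segment-assignment work. It needs no new imaging or patients and no change to the injection procedure. The downside is some misassignment at territory borders, confined to two-vessel patients, which could cancel the AUC gain if visual grading is accurate. Reporting the whole-heart result alongside lets the reader see whether the choice matters.

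### Does a rest scan taken the day after PCI spoil the ischemia measure that FFR is compared with?

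*Combined protocol and SAP*

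**What the plan says.** Under Study Design, the stress tracer is injected during FFR testing. PCI may come next: "A minimum of 2 mins will be allowed to elapse between radiotracer administration and percutaneous coronary intervention (PCI), if indicated", the stated reason being "to allow complete extraction of the radiotracer, and an accurate assessment of perfusion defect size". Stress images are acquired 1-3 hours after the angiogram, and the protocol explains why PCI in between does no harm: "Since the perfusion data will pertain to the time of tracer injection, patients could be vascularized as clinically indicated prior to the SPECT acquisition".

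The rest scan is covered by one sentence: "A low dose resting MPS will be performed the next day, if the stress MPS is abnormal". There is no separate rule for patients who had PCI. Those patients stay longer: "Patients will be monitored for 2-6 hours, or overnight, as clinically indicated following diagnostic coronary angiography and PCI, respectively".

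Under SPECT Analysis, the quantity to be analyzed is "Total Perfusion Defect size, which will be the parameter used for analysis". The section does not say whether this is the stress value or stress minus rest. Under Statistical Analysis, "An ROC curve analysis will be performed to define the cut-off of FFR that optimally predicts SPECT ischemia"; SPECT ischemia has no stated definition or threshold. The first aim is "To determine the correlation between FFR and ischemia (presence and extent) assessed simultaneously in the catheterization laboratory using regadenoson".

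**The concern.** The argument that an image shows perfusion at the moment of tracer injection protects the stress scan. Applied to the rest scan, the same argument puts resting perfusion after PCI. If ischemia is scored as the stress defect minus the rest defect, a treated patient with an abnormal stress scan has an intervention between the two halves of the score.

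The study is meant to remove timing differences between FFR and perfusion imaging, so this looks like a timing difference returning by another route. It may also be related to FFR. The Background section notes that practice treats FFR below 0.80 as significant, so PCI probably falls mainly on patients with low FFR, although the plan contains no written rule. An error concentrated in those patients could affect the correlation, the concordance percentage and the ROC cut-off.

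**Working it through.** The plan gives no figure to reproduce on this point, so the check is the order of events followed by simple algebra.

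**Order of events** for a patient with PCI and an abnormal stress scan (Study Design):

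1. FFR and stress tracer injection: before PCI.
2. PCI, at least 2 minutes later.
3. Stress acquisition at 1-3 hours: still shows the pre-PCI state.
4. Rest scan the next day: after PCI. That the rest tracer is given that day is inferred from the timing of the scan; it is not stated.

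**Who can be affected.** A patient with a normal stress scan has no rest scan. A patient without PCI has no intervention between the scans. Only patients with both an abnormal stress scan and PCI before the rest scan remain.

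**Size of the error in one such patient.** Let S be the stress defect size, R0 the rest defect that would have been seen before PCI, and R1 the rest defect seen the next day.

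- Stress-only score: S. Neither R0 nor R1 enters, so the error is 0.
- Stress-minus-rest score: recorded S − R1, wanted S − R0. Error = (S − R1) − (S − R0) = R0 − R1.
- If PCI leaves resting perfusion unchanged, R1 = R0 and the error is 0.
- If PCI relieves a resting defect, R1 < R0 and ischemia is overstated.
- If the procedure causes a new defect, R1 > R0 and ischemia is understated.
- If resting perfusion was normal before PCI, R0 = 0 and the error is −R1, which is 0 unless the procedure produced a defect.

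**Effect on concordance.** A patient's status changes only if the ischemia threshold lies between S − R0 and S − R1. Each change moves concordance by 1/50 = 2 percentage points.

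**How many.** The documents give neither a PCI rate nor an abnormal-scan rate. Assume that 10% to 40% of the 50 patients have both:

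- 0.10 × 50 = 5 patients; ceiling 5 × 2 = 10 points.
- 0.40 × 50 = 20 patients; ceiling 20 × 2 = 40 points.

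These ceilings require every exposed patient to change status in the same direction. They are not estimates. The number who would actually change status depends on R0 − R1, about which the documents say nothing. The effect on the correlation and on the ROC cut-off cannot be bounded from the documents either.

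**The case for a change.** The strongest case for a change is that stress minus rest is a realistic reading. Both aims and the ROC target speak of ischemia. The rest scan is taken exactly when the stress scan is abnormal, and no other use for it is stated. Patients with prior stents are eligible and prior infarction is not excluded, so resting defects cannot be assumed absent. Two analysts could therefore score the same patient differently, and one sentence written before results are seen would prevent that. Nor would it be an answer that the shift may be smaller than the sampling error with 50 patients: a systematic error is not excused by being smaller than a random one.

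Much of this stands. The sequence is as described, the wording is open, and the time-of-injection argument does not cover the rest scan. Three parts do not carry through.

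- The appeal to simultaneity is stretched. It most naturally concerns FFR and the stress injection. A resting scan cannot be simultaneous with hyperemic FFR, with or without PCI.
- The problem needs two conditions, that ischemia means a difference and that PCI alters resting perfusion. Neither is established.
- The available remedies show no gain. Recording PCI between the two injections changes nothing unless an analysis uses it. Repeating the analyses on stress defect size exchanges one impurity for another, because that measure includes fixed defects. A binary version would need a threshold for an abnormal stress scan, which the plan does not give. The stress values will exist for every patient scanned, so that analysis stays available without being written in now.

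**Conclusion.** No change follows. This is a missing detail that analysts can fill sensibly, not a demonstrated error. The natural reading of the one named parameter is the stress defect size: no subtraction is mentioned, and Study Design uses defect size for the stress injection. On that reading every patient's score is pre-PCI and the effect is exactly zero. The cost is that fixed and reversible defects are not separated, which is a separate limitation.

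On the stress-minus-rest reading, the mixed score arises only in patients with both an abnormal stress scan and PCI before the rest scan, and only where PCI changes resting perfusion. Each resulting change of status is worth 2 points of concordance. The number of such changes and their net direction are unknown.

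The definition of SPECT ischemia has to be fixed before any of the analyses can be run, and fixing it answers this question as well. The verdict rests on two assumptions: that the rest tracer is injected on the day of the rest scan, and that the named parameter is used as the text most simply reads. If the analysts do subtract rest from stress, the point becomes a caveat for interpreting results in treated patients.
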